### Farnesoid X receptor (FXR) agonist

Farnesoid X receptor (FXR) is a bile acid receptor, which is mainly expressed in the liver and intestine. FXR regulates synthesis, secretion and transport of bile acids (18). It has been considered as a promising target for the treatment of cholestatic disorders, including primary biliary cirrhosis (PBC) (19). FXR is also important for the regulation of the lipid and glucose metabolism (18). The activation of FXR showed beneficial effects on various metabolic diseases, including fatty liver diseases, type 2 diabetes, dyslipidemia, and obesity (18). Obeticholic acid (OCA), a FXR agonist, is proven as an effective drug for PBC (19). In 2016, OCA was approved in U.S. and Europe for the treatment of PBC. OCA is used together with another

medicine, ursodeoxycholic acid (UDCA), in patients who do not respond sufficiently to UDCA alone, and on its own in patients who cannot take UDCA. Now, phase III study for NASH is ongoing. In healthy volunteers, patients with primary biliary cholangitis (PBC) and patients with non-alcoholic steatohepatitis (NASH), single and multiple doses of obeticholic acid were well tolerated (19, 20). The most frequently reported adverse events considered to be drug-related were pruritus and fatigue (19, 20). Some abdominal pain and discomfort were reported. Based on a multiple-center phase III study in PBC patients, the recommended starting dosage of OCA is 5 mg orally once daily for 3 months with titration to 10 mg once daily based upon tolerability and response(21). In conclusion, obeticholic acid was found to be safe.

Recently, Friedman ES et al showed alteration of gut microbiome by OCA. In this study, male C57BL/6 mice were gavaged daily with water, vehicle, or OCA (10 mg/kg) for 2 weeks. Small intestine luminal contents were collected by flushing with saline and fecal pellets were collected at baseline and day 14. Culture experiments were performed to determine taxonomic-specific effects of bile acids and OCA on bacterial growth. As a result, administration of OCA dramatically led lower endogenous bile acid levels and an increased proportion of Firmicutes, specifically in the small intestine but not in stool, compared to control in mice (22). Friedman ES et al also conducted healthy volunteers on OCA doses of 5, 10 or 25mg/d and analyzed their microbiome in stool (22), however it is still unclear how the intestinal microbiome changes in human.

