## 5 Trial Medication / Drug

Generic Drug Name (& company brand name)	IMP or non-IMP	Used within Indication? (Y or N)	Route of administration (po,sc,iv,...)	Dose/dosage and units
Obeticholic acid (OCALIVA®)	IMP	N	po	10 mg
Placebo	IMP	N	po	placebo

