# 6 Safety

## Definitions

### 6.1 Adverse Event (AE)

An AE is any untoward medical occurrence in a patient, clinical investigation participant or participant of the treated group during an experiment who had been administered a pharmaceutical product, and which does not necessarily have a causal relationship with this treatment.

An AE can therefore be any unfavourable and unintended sign (including an abnormal laboratory finding), symptom or disease temporally associated with the use of a medicinal (investigational) product, whether or not considered to be related to the product. Any worsening (i.e. any clinically significant adverse change) in the frequency or intensity of a pre-existing condition, should be considered an AE.

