## 6.6 Safety Events that do not require reporting

In general, the following should not be reported as AEs:

- Pre-existing conditions, including those found as a result of screening (these should be reported as medical history or concomitant illness), unless the condition worsens during Trial treatment

The following AEs are commonly observed and expected, and/or are part of the well-known safety profile of OCALIVA® as documented in the Summary of Product Characteristics (SmPC) when used within the approved indication, and are therefore not considered adverse events for the purpose of the Trial:

- stomach pain
- feeling tired
- thyroid hormone irregularity
- dizziness
- fast or irregular heart beat (palpitations)
- pain in the mouth and throat
- constipation
- itchy, dry and/or red skin (eczema)
- rash
- pain in your joints
- swelling in the hands and feet
- fever

Although these events should not be reported to the Sponsor, these should be recorded in the participant's medical notes according to routine practice.

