## 6.7 Recording and Reporting of Safety Events

Investigators will seek information on the occurrence of safety events at each participant contact. All events, whether reported by the participant or noted by Trial staff, will be recorded in a timely manner in the participant's medical record and in the (e)CRF. If available, the *diagnosis* should be reported on the appropriate (S)AE page in the (e)CRF, rather than the individual signs or symptoms. If no diagnosis is available, the Investigator should record each sign and symptom as individual safety events.

The following minimum information should be recorded for each event:

- event description
- start and stop date of the event
- severity
- seriousness
- causality assessment to the IMP and/or Trial procedures
- outcome

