#### 6.7.6 Death

All deaths (except those defined under section 6.6) will be reported without delay to the Sponsor (irrespective of whether the death is related to disease progression, the IMP, participation in the experiment or an unrelated event). The Sponsor will notify all deaths as soon as possible after becoming aware to the central EC and the local EC of the concerned research site (via the contact person of the local research site, as applicable) and provide additional information if requested.

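### Section 6.6 exempts 12 known OCA effects from being adverse events, citing an indication this trial does not study, and conflicts with Sections 6.1, 6.7 and 6.7.2

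*Combined protocol and SAP*

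**What the plan says.** Section 6.6 exempts two kinds of event. The first is pre-existing conditions, which is unobjectionable. The second is a list of 12 effects: stomach pain, tiredness, thyroid irregularity, dizziness, palpitations, mouth and throat pain, constipation, eczema, rash, joint pain, swelling of hands and feet, and fever. These, it says, "are therefore not considered adverse events for the purpose of the Trial", and "these events should not be reported to the Sponsor". They are kept in the medical notes. The reason given is that they are expected, or belong to the known profile of OCALIVA "when used within the approved indication". The list carries no limit on severity or seriousness.

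Other sections say otherwise:

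- Section 5: in the drug table, the column "Used within Indication? (Y or N" has the entry N for obeticholic acid. Section 5.1 gives the indication as primary biliary cholangitis, and Section 2.4 places the trial in healthy individuals.
- Section 6.1: an AE is any unfavourable sign, symptom or disease "temporally associated with the use of a medicinal (investigational) product, whether or not considered to be related to the product".
- Section 6.7: "All events, whether reported by the participant or noted by Trial staff, will be recorded in a timely manner", in both the medical record and the (e)CRF.
- Section 6.7.2: all AEs on treatment and in the follow-up window are reported. The 6.6 list is not mentioned.
- Section 6.7.6: the rule on deaths begins "All deaths (except those defined under section 6.6", although 6.6 names no deaths.

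Section 1 adds, on earlier OCA studies: "The most frequently reported adverse events considered to be drug-related were pruritus and fatigue". It also mentions some abdominal pain and discomfort.

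**The concern.** The exempted effects are the ones the drug is already known to cause, so they are where a tolerability difference between OCA and placebo is most likely to appear. Being expected bears on how a serious reaction is classified for expedited reporting, which Section 6.8.1 assigns to the sponsor. It does not stop an event from being an AE.

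At stake is the AE record of healthy volunteers taking a drug outside its indication. If that record is later summarised, OCA could look better tolerated than it was. The counts would also depend on which of two conflicting instructions the staff applied.

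**Working it through.** **1. What the list covers.** The appendix on possible side effects names 2 effects as very common and 10 as common, besides pruritus. 2 + 10 = 12, and these are the same 12 as in Section 6.6. Pruritus is the only drug effect named there that is not exempt. Itch described as part of eczema is exempt, so whether itch is recorded depends on its label. Of the two most frequent drug-related events in Section 1, fatigue corresponds to an exempt item and pruritus does not.

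**2. Whether the stated reason applies.** Section 6.6 relies on use within the approved indication. Sections 5, 5.1 and 2.4 together show that this use is outside it. The reason does not carry over.

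**3. The rules side by side, for a non-serious listed event such as tiredness on day 10 of a treatment period.**

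| Section | Is it an AE? | Where does it go? |
|---|---|---|
| 6.1 | Yes, whatever the cause | not addressed |
| 6.6 | No | Medical notes, not the sponsor |
| 6.7 | Treated as a safety event | Medical record and (e)CRF |
| 6.7.2 | Yes, if 6.1 defines it | Reported |

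Neither 6.7 nor 6.7.2 makes an exception for 6.6, so the conflict is not resolved in the text. The grading in 6.7.1 adds to it: the highest causality grade requires that the event be a listed possible reaction, and 6.6 removes all but one of the drug effects that the appendix lists.

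**4. Effect on the data.** Let r be the fraction of non-serious listed events that reach the AE data, taken as equal in both periods. Then the recorded OCA-minus-placebo difference = r × the true difference. If 6.6 is always followed, r = 0; if 6.7 is always followed, r = 1. The documents do not fix r.

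**5. Size.** The plan gives no figure on this point. The only rates are the bands printed in the appendix: 1 in 100 to 1 in 10 for two effects (v), and 1 in 1000 to 1 in 100 for ten (c). They come from product information for the approved use, with no placebo rate. They are also inconsistent, since the appendix calls itching very common at more than 1 in 10. They serve here only as an assumed range for 21 days on OCA.

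Expected listed events in n people = n × (2v + 10c):

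- n = 12, low: 12 × (0.02 + 0.01) = 0.36
- n = 12, high: 12 × (0.20 + 0.10) = 3.6
- n = 10 (the number the plan expects to complete): 0.30 to 3.0

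People with at least one listed event, if events are independent: 1 − (1 − v)² × (1 − c)¹⁰ = 0.0297 (low) or 0.2675 (high), so about 0.4 to 3.2 of 12. The chance that at least one of 12 is affected runs from 30% to 98%. That range is too wide to be an estimate. It shows only that lost events are plausible.

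**The case against.** The best defence is that 6.6, by its heading, concerns reporting only, while 6.7 governs recording. On that reading the events are in the eCRF by period and only the transfer to the sponsor is waived. That transfer matters less here, since the synopsis shows one site and the coordinating investigator holds both investigator and sponsor responsibilities. This reading does not fit the words "are therefore not considered adverse events for the purpose of the Trial", which take the events out of the AE category altogether. But 6.7 does send all events to the eCRF, so a reader who inferred that the recorded difference on these terms must be zero would go too far. Zero is the result only if 6.6 is followed throughout, and even then the events could be retrieved from the medical notes.

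A reader might also infer that serious listed events, or deaths, would go unreported. The documents do not support that. Section 6.3 defines a serious event independently of the list, 6.7.2 requires every one within 24 hours, and 6.7.1 requires seriousness to be assessed for all safety events. The reporting overview in 6.8.3 does allow unspecified exceptions for serious events, which leaves a little ambiguity. The exception in 6.7.6 has nothing to act on, and 6.8.3 lists deaths without it.

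Three further objections stand. Safety is not an objective or endpoint, and the efficacy table in 7.2.1 has no AE analysis, so no planned result is shown to be biased. Section 1 reports good tolerability in healthy volunteers as well as patients, although 6.6 does not rely on it and no rates are given. And the bands used for size come from the same approved-use profile that is rejected as a basis for 6.6.

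**Conclusion.** The point holds as an unresolved conflict with a one-sided risk. For non-serious listed events, following 6.6 hides any OCA excess and following 6.7 preserves it; the protocol does not say which prevails. The justification offered for 6.6 does not apply to this use.

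The size of any understatement is unknown. About 0.4 to 3.6 listed events in 12 people on OCA is an assumed range, not an estimate. It counts all listed events on OCA, not the excess over placebo, and the exemption covers placebo periods too.

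The hunger comparison is not affected. Section 7 defers detail to a separate SAP that may define an AE table, but no table can show events kept out of the AE data. The wording should be corrected, though the primary result does not depend on it.

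**What to change.** 1. In 6.6, keep only the exemption for pre-existing conditions. Delete the list of 12 effects, its introduction and the sentence after it. Record these events as AEs in the eCRF under 6.7.
2. In 6.7.6, delete the bracketed exception that refers to 6.6.
3. Leave expectedness to the sponsor's assessment in 6.8.1.
4. In 7.2 and the SAP, add a descriptive AE summary by treatment period for everyone who took at least one dose, without tests. Section 7.2 at present names only those who completed the study.

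No new measurement is needed, since 6.7 already has investigators ask about safety events at every contact. The cost is the change of wording and a few more eCRF entries: on the assumed range about 0.4 to 3.6 in the OCA periods, plus background events in both periods.

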## 6.7 Recording and Reporting of Safety Events

Investigators will seek information on the occurrence of safety events at each participant contact. All events, whether reported by the participant or noted by Trial staff, will be recorded in a timely manner in the participant's medical record and in the (e)CRF. If available, the *diagnosis* should be reported on the appropriate (S)AE page in the (e)CRF, rather than the individual signs or symptoms. If no diagnosis is available, the Investigator should record each sign and symptom as individual safety events.

The following minimum information should be recorded for each event:

- event description
- start and stop date of the event
- severity
- seriousness
- causality assessment to the IMP and/or Trial procedures
- outcome

### 6.7.1 Assessment

All safety events must be evaluated by an Investigator with regards to:

- **Seriousness:** determine whether the AE is an SAE. See above for the seriousness criteria.
- **Severity:**
  - Severity grading must be evaluated by the Investigator according to the current version of the National Cancer Institute (NCI) Common Terminology Criteria for Adverse Events (CTCAE, most recent version)
  - Severity must be evaluated by the Investigator according to the following definitions:

- *Mild* – no or transient symptoms, no interference with the participant's daily activities
- *Moderate* – marked symptoms, moderate interference with the participant's daily activities
- *Severe* – considerable interference with the participant's daily activities, unacceptable

▪ **Causality:**

- *None* – The AE is not related to the IMP or participation in the experiment
- *Unlikely* – It is unlikely that the AE is related to the IMP or participation in the experiment; an alternative explanation is more likely (e.g. concomitant medication(s), concomitant disease(s)), and/or the relationship in time suggests that a causal relationship is unlikely
- *Possible* – The AE might be due to the use of the IMP or participation in the experiment. An alternative explanation is inconclusive. The relationship in time is reasonable; therefore the causal relationship cannot be ruled out
- *Probable* - The AE might be due to the use of the IMP or participation in the experiment. The relationship in time is suggestive (e.g. confirmed by dechallenge). An alternative explanation is less likely
- *Definitely* – The AE is listed as a possible adverse reaction and cannot be reasonably explained by an alternative explanation. The relationship in time is very suggestive (e.g. it is confirmed by dechallenge and rechallenge)

### 6.7.2 Timelines for reporting

After obtaining informed consent and prior to initiation of Trial treatment, only (serious) adverse events caused by a Trial specific procedure should be reported in the (e)CRF.

After initiation of Trial treatment, safety events will be reported as follows:

- All AEs, SAEs and AESIs occurring during Trial treatment or within 30 days after last Trial treatment administration, or last follow-up visit (whichever occurs first) will be reported.
- All SAEs and AESIs as defined in the protocol must be reported to the Sponsor within 24 hours of the Trial staff becoming aware of the event. The initial report shall be followed by detailed, written reports. Both the initial and follow-up reports shall identify participants only by their Trial-specific identification.
- SAE details will be reported by the Investigator to the Sponsor:
  - By completing the SAE form in the (e)CRF
  - If an authorised Investigator from the reporting site is unavailable, initial reports without causality and expectedness assessment should be submitted to the Sponsor by a healthcare professional within 24 hours of becoming aware of the SAE, but must be followed-up by a medical assessment performed by an authorised Investigator, as soon as possible thereafter.

### 6.7.3 Follow-up

The Investigator must record follow-up information by updating the participant's medical records and the appropriate form(s) in the (e)CRF.

SAE follow-up information should only include new information (e.g. corrections or additions) and must be reported within 24 hours of the Investigator's first awareness of the information. This is also the case for previously non-serious AEs which subsequently become SAEs.

- All **SAEs** must be followed until the outcome of the event is 'recovered', 'recovered with sequelae', 'not recovered' (in case of death due to another cause than the SAE) and until all related queries have been resolved, or until the end of the Trial (whichever occurs first)
- **Non-serious AEs** must be followed until the participant's last Trial visit, and until all related queries have been resolved

**SAEs after the end of the Trial:** If the Investigator or Trial team becomes aware of an SAE with suspected causal relationship to the IMP or experiment, after the participant has ended the Trial, than this SAE must be reported within the same timelines as for SAEs occurring during the Trial.

#### 6.7.4 Pregnancy

Female participants must be instructed to notify the Investigator immediately if they become pregnant during the Trial. The Investigator must report to the Sponsor, any pregnancy in participants who have received Trial product(s).

#### 6.7.5 Technical Complaints

Technical complaints with the IMP or comparator treatment should be reported to the Sponsor and to the Marketing Authorisation Holder (MAH) (e.g. change in colour, unequal sizes, broken vials/pills, sedimentation, inconsistent packaging or labelling etc.). If the technical issue puts the safety of Trial participants at risks and/or jeopardises the integrity of the Trial (e.g. when the issue causes unblinding), than the Ethics Committee must be notified immediately and no later than 24 hours of the Trial team becoming aware.

#### 6.7.6 Death

All deaths (except those defined under section 6.6) will be reported without delay to the Sponsor (irrespective of whether the death is related to disease progression, the IMP, participation in the experiment or an unrelated event). The Sponsor will notify all deaths as soon as possible after becoming aware to the central EC and the local EC of the concerned research site (via the contact person of the local research site, as applicable) and provide additional information if requested.

### 6.8 Reporting requirements to Ethics Committees (ECs) and Competent Authorities (CAs)

The Investigator is responsible for ensuring that all safety events are recorded in the (e)CRF and reported to the Sponsor in accordance with instructions provided in the protocol.

The Sponsor will promptly evaluate all SAEs and AESIs against medical experience to identify and expeditiously communicate possible new safety findings to Investigators, EC(s) and applicable CA(s) and participants as appropriate, in accordance with applicable legislation.

#### 6.8.1 Sponsor's reporting of Suspected Unexpected Serious Adverse Reactions (SUSARs)

After receiving the SAE report form from the Investigator, the Sponsor must perform a causality (relationship) assessment. The term Serious Adverse Drug Reaction (SADR) is to be used whenever either the Investigator or the Sponsor deems the SAE is possibly or probably related to the IMP.

The Sponsor must evaluate (and document the evaluation of) the expectedness for each SADR against the Reference Safety Information, e.g. the Investigator's Brochure or applicable product information. In case the event is Unexpected (i.e. a SUSAR) it must be reported by the Sponsor to the EC(s), CA(s) (through the EudraVigilance database or other local process) and other participating Investigators using the Council for International Organizations of Medical Sciences (CIOMS) form within the following timelines:

- **7 calendar days** if the event is fatal or life-threatening (follow-up information to be provided within an additional 8 calendar days)
- **15 calendar days** if non-fatal or non-life-threatening event (follow-up information be provided as soon as possible)

#### 6.8.2 Annual reporting

It is the Sponsor's legal obligation to, at least once a year and for as long as the clinical Trial runs (or ad hoc on request), submit a progress report to the EC(s) and CA(s) containing an overview of all Serious Adverse Reactions (SARs) that occurred during the reporting period and taking into account all new available safety information received during the reporting period. This information can be communicated as part of the Annual Progress Report (APR) or as a separate Development Safety Update Report (DSUR, cfr. ICH E2F) or an Annual Safety Report (ASR)

#### 6.8.3 Overview reporting requirements

WHO	WHAT	HOW	TO	TIMELINES
-----	------	-----	----	-----------

	AE	AE form	Sponsor	as defined in protocol
Investigator	SAE	SAE form	Sponsor	Initial & follow-up information: Immediately (within 24 hours of becoming aware of the event) Exceptions: as defined in protocol
	Death	SAE form	Sponsor	asap
Sponsor	SUSAR	CIOMS form: - EC-reporting: according to EC process - Reporting to CA(s): through EudraVigilance or local CA process	Unblinded report: - EC(s) - CA(s) - MAH (if applicable) Blinded report to: - PI's of participating sites	For fatal or life-threatening SUSAR: asap, but no later than: - 7 calendar days (initial report) - 8 calendar days (follow-up report) For non-fatal and non-life-threatening SUSAR: - 15 calendar days (initial report) - asap (follow-up report)
	Death	SAE form + narrative	- EC(s)	asap
	Annual Progress/ Safety Report	DSUR or APR/ASR template	- EC(s) - CA(s) participating countries	annually

